1 PROTOCOL SUMMARY

1.1 SYNOPSIS

Title:	Strategy-based cognitive intervention for Parkinson Disease: A pilot randomized controlled trial. Aka: MultiContext Approach for Parkinson Disease (MC4PD) Pilot
Grant Number:	R21 AG063974
Study Description:	We have developed a strategy-based cognitive intervention, based on the MultiContext (MC) approach, to enable people with PD to apply strategies in their everyday lives to cope with cognitive decline and improve or maintain daily function. We hypothesize that this intervention will produce better functional outcomes compared to cognitive process training. This project will assess feasibility and treatment fidelity and generate data in preparation for a definitive clinical trial by conducting a single-blind pilot randomized controlled trial comparing the MC approach to a standard-of-care treatment (Control). Participants with PD without dementia (N = 60) will complete pre-treatment testing, randomization to treatment group, 10 treatment sessions, and immediate and 3 months post-treatment testing.
Objectives:	Aim 1: Examine the feasibility of the MC approach for people with PD within an RCT. Aim 2: Demonstrate adequate treatment fidelity to the MC approach. Aim 3: Obtain preliminary estimates of the MC approach's effect on patient-reported functional cognition.
Endpoints:	Aim 1 Endpoints: Recruitment rate (#/month); retention rate; % of participants completing the intervention in 12 weeks Aim 2 Endpoints: Therapist adherence and competence scores; Client Satisfaction Questionnaire; Pittsburgh Rehabilitation Participation Scale Aim 3: Bangor Goal Setting Interview
Study Population:	60 males and females over age 40 who meet criteria for typical idiopathic PD, are stage I-III, and do not have dementia.
Phase or Stage:	Stage I (generation, refinement, modification, adaptation, pilot testing)
Sites/Facilities Enrolling Participants:	Washington University School of Medicine in St. Louis
Description of Study Intervention/Experimental Manipulation:	Both the MC and Control intervention will consist of 10 1-1.5 hour sessions over 12 weeks delivered in an individual, face-to-face format by trained licensed occupational therapists. Both interventions involve collaborative client-centered goal setting, practice of cognitively challenging functional activities, and home practice assignments. The MC intervention additionally incorporates strategy training, a metacognitive framework, therapist mediation, and action planning.
Study Duration:	24 months
Participant Duration:	14 weeks of in-person participation with a 3 month follow-up; 26 weeks in total

1.2 SCHEMA

The following target interval limits will be used, expressed as “target (window)”:

- Pre assessment will occur \leq 14 days of screening for eligibility. If more than 14 days have passed, participants will be re-screened before enrollment.
- Treatment Session 1 will occur 7 (5-14) days after the Pre assessment.
- Each subsequent treatment session will occur 7 (5-9) days after the prior treatment session.
- Post assessment will occur 7 (5-14) days after Treatment Session 10.
- Follow-up assessment will occur 3 months (-7 days/+14 days) after Treatment Session 10.

Keep in mind that these are targets, and this study aims to determine whether these targets are feasible and/or how we can improve our processes to meet them in the future. Although we aim for participants to have a treatment session each calendar week, the stated goal of completing the intervention within 12 weeks allows for up to 2 missed weeks due to practical circumstances (that would be present in real-world clinical practice) such as participant or therapist illness, travel, inclement weather, holidays, etc.

1.3 SCHEDULE OF ACTIVITIES

	Pre-screening (Pre-consent)	Visit 1: Pre-treatment assessment	Intervention Sessions		Visit 12: Post-Treatment Assessment	Visit 13: Follow-up Assessment
			Visit 2-3: OT Eval	Visits 4-11: OT Treatment		
Inclusion/Exclusion criteria	X	X				
Informed Consent		X				
Baseline Characteristics						
Demographics		X				
Clinical characteristics		X				
UPDRS III		X				
NIH Toolbox Cognitive Battery		X				
MoCA	X+	X				
Web or mailed questionnaires	MDS-UPDRS II		X			
	Beck Depression Inventory-II		X			
	Parkinson Anxiety Scale		X			
	Apathy Scale		X			
	Parkinson Fatigue Scale		X			
Randomization		X				
Primary Outcomes						
2a. Therapist Adherence & Proficiency*			X (random 30% of sessions rated)			
2b. Client Satisfaction Questionnaire					X [#]	
2b. Pittsburgh Rehabilitation Participation Scale*				X (3 sessions/pt)		
2b. Homework adherence*				X		
3. Bangor Goal Setting Interview [^]			X		X [#]	X [#]
Secondary/Exploratory Outcomes						
Weekly Calendar Planning Activity			X		X	
Self-Regulation Skills Inventory			X		X	
NeuroQOL Cognitive Function		X			X	X [#]
NeuroQOL Participation (Ability)		X			X	X [#]
Web or mailed questionnaires	Global Rating of Change				X	X
	PD-Cognitive Functional Rating Scale [^]		X		X	X
	Cognitive Self-Efficacy Scale		X		X	X
	General Self-Efficacy Scale		X		X	X
Credibility & Expectancy Questionnaire			X	X (in 4 and 7)	X [#]	
Adverse Events Reporting			X	X	X	

Notes: * Completed by blind raters based on audiotape data (therapist adherence & competence; rehab participation) or homework worksheet. [^] Informants also complete these measures. [#] Collected by web or mailed questionnaires. + Phone/blind version.

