10.2 PROTOCOL AMENDMENT HISTORY

*The table below is intended to capture changes of versions of the protocol, including a description of the change and rationale. A **Summary of Changes** table for the current amendment is located in the **Protocol Title Page**.*

Version	Date	Description of Change	Brief Rationale
2	May 2020	Changed randomization process and related communication among team members	To remove PI from randomization process and blind her to study group; minimize bias
2	May 2020	All participants will undergo 10 treatment sessions	To ensure treatment groups are balanced on dose of intervention
2	May 2020	Changed definition of screen failure from what was initially provided by this template	Study monitor request
2	May 2020	Added criteria used to declare failure for each aim to Objectives and Endpoints section	To enhance rigor and inform decision-making for next steps
2	May 2020	Specified target interval limits for timing of assessment and treatment sessions (see Schema)	To enhance rigor
2	May 2020	Added question to AE report form to monitor for psychological risks	A stated risk of the study, needed to capture it
2	May 2020	Added a question to the Follow-up assessment to monitor for perceived confidentiality breach	A stated risk of the study, needed to capture it
3	Nov 2020	Fixed Schedule of Activities table to indicate that inclusion/exclusion criteria are assessed in Visit 1 (via MoCA); consent form will also be modified to include this information	To fix a prior inconsistency pointed out by study monitor
4	Dec 2020	Added phone/blind MoCA to screening phone call	To reduce risk of enrolling people who do not meet cognitive criteria for entry
4	Dec 2020	Specified randomization ratio changes over course of study	To enhance transparency
5	May 2021	Added note that participants excluded post-randomization count as failures in retention endpoints	To enhance rigor and transparency

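### Scheduled adverse event reporting ends at Post, leaving about 12 of 26 weeks, up to the 3-month Follow-up survey, with no planned elicitation

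*Combined protocol and SAP*

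**What the plan says.** In the Section 1.3 table, the row "Adverse Events Reporting" carries a mark for the two OT evaluation visits, the eight OT treatment visits and the Post visit. The cells for Visit 1 and Visit 13 are empty.

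Participation does not end at Post. The Synopsis gives "14 weeks of in-person participation with a 3 month follow-up; 26 weeks in total", and Section 4.4 defines study completion by the 3-month assessment. The Schema says "Follow-up assessment will occur 3 months (-7 days/+14 days) after Treatment Session 10". Section 8.1 makes that contact a web or mailed survey, and Section 1.3 places on it the Bangor goal ratings, the NeuroQOL scales, the global rating of change, the PD cognitive functional rating scale and both self-efficacy scales.

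The version 2 entry in Section 10.2 reads "Added question to AE report form to monitor for psychological risks", on the ground that this was a stated risk that had to be captured. A companion entry, with the same rationale, put a confidentiality question into the Follow-up assessment; Section 10.1.3 gives its wording.

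Sections 2.3, 8.2, 8.3, 8.4 and 10.1.4 refer risk, safety assessments, AEs, unanticipated problems and safety oversight to a Data & Safety Monitoring Plan, which is not among the documents.

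**The concern.** The plan follows goal attainment for three months after treatment but schedules questions about harm only until about one week after it. A site working from the table would not ask about AEs over the interval in which durability of effect is estimated (H3, exploratory).

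The psychological-risk item is the sharpest case. The sponsor considered that risk worth a dedicated question, but because the question is part of the AE form it is last asked when the form is. No other scheduled instrument takes its place: the depression and anxiety scales appear only as baseline measures.

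The arms also differ in a way that could bear on this risk. Sections 2.2 and 6.1.1 describe MC as building awareness of deficits, while the Control description has test scores reviewed without any awareness-building discussion. That psychological effects might therefore differ by arm is an inference from the design; the documents do not say so. It is still a reason to ask both arms the same question for as long as outcomes are measured.

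**Working it through.** **Inputs**
- Total and in-person duration (Section 1.1): 26 and 14 weeks.
- Pre to Session 1 (Section 1.2): "Treatment Session 1 will occur 7 (5-14) days after the Pre assessment".
- Between sessions, 9 intervals (Section 1.2): "Each subsequent treatment session will occur 7 (5-9) days after the prior treatment session".
- Intervention length (Section 1.2): "the stated goal of completing the intervention within 12 weeks allows for up to 2 missed weeks due to practical circumstances".
- Session 10 to Post (Section 1.2): "Post assessment will occur 7 (5-14) days after Treatment Session 10".
- Session 10 to Follow-up (Section 1.2): 3 months, −7/+14 days. Assumption: 3 months = 91.3 days.

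**1. Reproduce the stated durations.** In person: 1 + 12 + 1 = 14 weeks. Total: 1 + 12 + 91.3/7 = 1 + 12 + 13.04 = 26.04, which rounds to the stated 26 weeks. The Synopsis and Schema agree.

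**2. Gap from the stated durations.** 26 − 14 = 12 weeks; 12/26 = 46% of participation.

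**3. Gap at target timing, no missed weeks.** Session 10 falls on day 7 + 9 × 7 = 70, Post on day 77 and Follow-up on day 70 + 91.3 = 161.3. The gap is 161.3 − 77 = 84.3 days = 12.0 weeks, or 84.3/161.3 = 52% of a 23.0-week participation.

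**4. Gap across the visit windows.**
- Shortest: (91.3 − 7) − 14 = 70.3 days = 10.0 weeks.
- Longest: (91.3 + 14) − 5 = 100.3 days = 14.3 weeks.
- Lowest share: Session 10 on day 14 + 9 × 9 = 95, so 70.3/(95 + 84.3) = 39%.
- Highest share: Session 10 on day 5 + 9 × 5 = 50, so 100.3/(50 + 105.3) = 65%.

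**5. Is the blank cell real?** Read column by column, the AE row has the same pattern of marked columns as the Credibility & Expectancy row, which also ends at Visit 12. The Bangor row, read the same way, does show a mark at Visit 13. A lost mark in the AE row is therefore unlikely.

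**6. Two stated risks side by side.** Version 2 added one question for each, with the same rationale. The confidentiality question went into Follow-up. The psychological question went onto the AE form, whose last scheduled use is Post. The schedule thus asks about one stated risk at three months and not the other.

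**The case against.** The strongest reply is that a blank cell shows only that no elicitation is scheduled. AE procedures belong to the Data & Safety Monitoring Plan, which may define a longer reporting period or duties for spontaneous and serious events. Section 7.2 also requires the reason to be documented when a participant is withdrawn because of an event or medical condition. This stands. A reader might infer that harms after Post are not collected, or that a late event has no chance of being recorded; the documents support neither.

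Second, safety is not an aim or endpoint, H3 is exploratory, and Sections 9.2 and 9.4 disclaim any intent to demonstrate efficacy. Ending solicited AE collection soon after the last therapy session can be defended as a design choice. This limits the consequence, but it does not explain why an available contact should leave the question out.

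Third, a reader might want the probability that a late event is missed. That needs an event rate, which the documents do not give. With 51 retained (85% of 60), the chance that at least one participant has an event is 1 − 0.99^51 = 40% at an assumed 1% rate and 1 − 0.98^51 = 64% at 2%. The assumption sets the answer, so no such figure is relied on.

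Fourth, a reader might extend the point to Visit 1 and to early stoppers. Little is gained there. Session 1 follows Visit 1 by 5 to 14 days and already carries AE reporting. Under Section 7.1, those who stop treatment but stay in the study still have a Post assessment, where AE reporting is marked.

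**Conclusion.** The point holds as one about scheduling. As printed, the Schedule of Activities elicits AEs through Post only, leaving about 12 of 26 weeks (46%; about 10 to 14 weeks across the windows) with no scheduled AE question, including the psychological-risk item. Outcomes are measured at the end of that interval through a survey that could carry the form.

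This rests on the table having been read correctly, on 3 months being taken as 91.3 days, and on the AE form being used only where its row is marked. It does not establish that later harms go unrecorded, and it does not threaten Aims 1 to 3. It is an inexpensive improvement, and the need to act does not depend on the unseen monitoring plan: if that plan stops at Post, collection should be extended; if it runs to Follow-up, the schedule disagrees with it and the two must be reconciled.

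**What to change.** - Mark Adverse Events Reporting at Visit 13 in Section 1.3.
- Add the existing AE report form, with its psychological-risk question, to the Follow-up web or mailed survey, with a recall period that starts at the participant's last study visit.
- State that AEs will be reported by arm through Follow-up. Section 9.4 currently covers Aims 1 to 3 only.
- State the AE collection period once and make the schedule and the Data & Safety Monitoring Plan agree on it.

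The cost is a minor amendment: one table row, one existing form added to one existing survey, a few more minutes for each participant, and some unrelated PD events to classify. Section 10.2 records an earlier correction to this same table (version 3) after the study monitor pointed out an inconsistency, so there is a precedent for such a change.

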2 INTRODUCTION

2.1 STUDY RATIONALE

Parkinson disease (PD) affects over 1 million Americans and causes considerable personal and socioeconomic costs (>\$34 billion/year in the US) that are expected to rise as the population ages¹. Cognitive impairment produces disability and reduced quality of life among non-demented people with PD²⁻⁴. Surgical and pharmacologic treatments for PD do not prevent or treat cognitive impairment and may even exacerbate the problem⁵⁻⁸. As such, cognitive rehabilitation treatments that mitigate its negative functional consequences are a top research priority⁸⁻¹³. Unfortunately, existing cognitive rehabilitative programs for PD, which focus on restoring deficient cognitive processes through **process training** (repetitive practice of tasks that challenge specific cognitive processes), have had limited effect on daily function¹⁰. To overcome this limitation, we take a **strategy training** approach. We teach people targeted strategies to use in everyday life to circumvent cognitive deficits and accomplish meaningful daily activities. Contemporary cognitive rehabilitation evidence supports this approach for people with chronic neurocognitive dysfunction from stroke and brain injury¹⁴⁻¹⁶; however, it has not been studied in PD. By teaching strategies for everyday cognition and using training techniques to support transfer of learning beyond the training context, we hypothesize that our strategy training interventions will produce better functional outcomes for people with PD compared to process training.

We adapted the MultiContext (MC) Approach to enable people with PD to apply strategies in their everyday lives to cope with cognitive decline and improve or maintain daily function. The MC Approach is an individualized, community-based intervention that focuses on the attainment of personally meaningful functional goals using training techniques known to enhance strategy learning and transfer.

We hypothesize that the MC Approach can enable people with PD to manage everyday cognitive challenges so they can perform and participate in desired activities and roles. Such an intervention could improve function and quality of life, reduce caregiver burden, and enhance clinical care for this population. This specific study is part of a rigorous developmental process designed to optimize the MC Approach for clinical trials and eventual translation into clinical practice. It is **significant** because it will provide us with feasibility data, fidelity enhancements, clinical trials infrastructure, experience training and monitoring therapists, and an estimate of treatment effect—all essential elements for efficiency, rigor, reproducibility, and payoff in future clinical trials as well as for implementation and sustainability in real-world clinical practice.

2.2 BACKGROUND

We need effective cognitive interventions for people with PD. About one third of people in the earliest stages of PD demonstrate mild cognitive deficits—typically in memory and executive control functions—which are attributed to frontostriatal circuitry dysfunction due to dopamine depletion in the basal ganglia and prefrontal cortex^{5,17,18}. These deficits produce disability, reduced quality of life, and restricted participation early in the course of PD, potentially to a larger extent than motor impairment^{2-4,19,20}. Due

to its negative impact on daily function and the fact that it does not respond to existing medical treatments, cognitive impairment is considered a major unmet need and important target for treatment by patients, families, practitioners, and scientists in the PD community^{8,9}.

Cognitive process training interventions do not improve daily function in PD. Almost all cognitive interventions for PD to date have taken a restorative process training approach, attempting to enhance underlying neural physiology and improve specific cognitive processes through practice^{10,21-25}. Although this approach has produced small, specific, and short-term improvements on cognitive tests, these benefits do not translate to daily function¹⁰. The goal of cognitive rehabilitation is to enable people with cognitive dysfunction to perform and participate in meaningful everyday activities and roles^{15,26}. Clearly, cognitive process training falls short of this goal for people with PD, so we should pursue a different approach.

Strategy training interventions may improve daily function in PD. A strategy training approach to cognitive intervention provides ways to maintain task performance despite the presence of cognitive deficits. It involves teaching people to use metacognitive, compensatory or adaptive techniques to bypass cognitive processing limitations and achieve task-related goals²⁷. Strategy training is recommended for those with mild (vs. more severe) cognitive decline because it requires learning, capitalizes on existing cognitive resources, and aims to prevent or delay functional decline^{27,28}. Although strategy training does not specifically target neurodegeneration or aim to improve cognition per se (which may be unrealistic in the context of neurodegeneration²⁹), it can facilitate metacognitive control and continued activity engagement which may promote neuroplasticity, maintain cognition, or slow cognitive decline³⁰⁻³². Strategy training is a Practice Standard for rehabilitation of mild memory and executive function deficits after stroke or brain injury¹⁴, and it has a larger impact on daily function than process training in older adults with MCI^{29,33}. Because people with PD-MCI have similar cognitive problems and cognitive rehabilitation goals as these populations, strategy training may also be beneficial for them^{34,35}; however, its application in PD is very limited to date^{10,13}. Our prior work in prospective memory supports the value of strategy training for non-demented people with PD for improving objective laboratory performance³⁶ and maintaining reported everyday performance³⁷.

We adapted the MultiContext (MC) Approach to teach non-demented people with PD strategies in a way that promotes generalization to daily function. In contrast to process training, which can produce skills that are tightly tied to the training context, strategy training can produce flexible skills that people can apply across situations if it uses training techniques that foster transfer of learned strategies to real-world activities and goals^{38,39}. The MC Approach includes such techniques. First, it is client-directed in that the person identifies his or her own treatment priorities (goals), selects the treatment session focus, develops strategies to test, and is considered the expert in his or her own situation. Second, it uses a metacognitive framework to promote awareness of deficits and teach people to use structured and explicit methods to solve performance problems by anticipating challenges, generating and testing strategies or solutions, monitoring and evaluating their effectiveness during performance, and making connections between activity experiences and contexts (which facilitates generalization³⁹⁻⁴²). The therapist role within this client-directed metacognitive approach is to guide the process of self-awareness, strategy generation, and generalization. The therapist does not “tell” the person what to do, but instead

uses mediation (e.g. systematic questioning, prompts) to facilitate reflection and discovery. The above techniques are rooted in constructivism theories that suggest learning and transfer are enhanced when the learner actively engages in the process of discovering, testing, and evaluating solutions to challenging experiences⁴³⁻⁴⁶. Emerging evidence in older adults^{27,47,48} and neurological conditions^{16,49,50} increasingly supports the superiority of this type of approach over more directed training approaches. Finally, the MC Approach uses homework with action plans, which are effective tools in promoting behavior change, self-efficacy and daily function^{51,52}, to support strategy application in everyday life³⁸. Our preliminary study⁵³ found that the MC Approach is acceptable, engaging, and may address the functional cognitive problems of people with PD.

Treatment fidelity is critical to complex behavioral interventions. Treatment fidelity—methods used to ensure interventions are implemented as intended—is increasingly recognized as essential to behavioral intervention development^{54,55}. High treatment fidelity increases the ability to attribute change (or lack thereof) in outcomes to the intervention per se (rather than, e.g., implementation failure), facilitates theory testing, improves retention, is associated with better treatment outcomes, and enhances reproducibility and translation of interventions from research to real-world settings⁵⁶. Therefore, in accordance with the NIH Behavioral Change Consortium Treatment Fidelity Workgroup guidelines^{54,57} we developed processes to enhance and monitor treatment fidelity, and we will assess and optimize their effectiveness in this study (**Aim 2**).

